² Informed Consent must be obtained before any trial related procedures. Procedures or tests that are performed as a part of standard clinical care prior to informed consent, and therefore, not for the purpose of the trial, do not need to be repeated at screening if they have been performed within the allowed screening timelines. In these cases, source documents must show that these procedures or tests were performed as standard clinical practice and not for the purpose of the present trial. In case the indwelling intracerebroventricular access device (e.g. Ommaya) is placed in connection with the tumor resection, the informed consent must be obtained prior to the surgery and can be done before the start of the screening period if necessary. The investigator is responsible for documenting this properly.

³ Thyroid stimulating hormone (TSH)/ free and total T4 to be assessed at screening, pre-dose week 1 and 4, pre-dose week 5 and 8, week 26 if applicable and weeks 52, 78, 104 130 and 156.

⁴ Measurements of pulse oximetry, heart rate, respiratory rate, temperature, and blood pressure.

⁵ To be performed within 3 weeks prior first IMP infusion.

⁶ Lansky Scale < 16 years, Karnofsky Scale \geq 16 years. Post week 26 every 6 months.

⁷ (Magnetic resonance imaging of the brain and spine to be completed before first IMP administration), at week 4 (\pm 4 days), 8 (\pm 4 days) and 26 (\pm 24-29 weeks)

⁸ Gross investigation of cranial nerves by physical examination and radiographical investigation as described in section 6.1.3. Evaluating neurological Adverse Events (AEs), the National Cancer Institute clinical neurotoxicity criteria will be used. Any patient that develops a Grade 4 neurotoxicity must be discontinued from treatment. The clinical neurotoxicity evaluation is to be conducted at screening and weeks 1, 4, 5, 8 and 26. The radiographic assessment of neurotoxicity and disease progression (by MRI) is to be conducted at screening, weeks 4 and 8 and week 26.

⁹ Only for patients who do not have an intracerebroventricular device already placed. The procedure must be conducted prior to first dose and after the patient has been assessed to be eligible to enter the trial.

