¹⁰ If CSF sample is positive for abnormal cells or outside reference ranges for any of the following: 1. total protein 2. glucose 3. cell count, it must be repeated within 4 weeks of the sample at screening. If abnormal CSF glucose (CTCAE \geq Grade 2) is obtained, a fasting serum glucose is to be obtained at next patient visit. At week 26, the CSF analysis should include cytology only.

¹¹ Treatment with potassium iodide and Cytomel should be initiated 1 week prior to each ¹³¹I- omburtamab infusion in a cycle and continue until 2 weeks after ¹³¹I- omburtamab infusion in the same cycle..

¹² Thyroid protection should be initiated 1 week prior to IMP administration. See section 7.2.5 for further details.

¹³ Thyroid protection should be initiated 1 week prior to next IMP administration – this is only applicable for week 4 and not week 8. See section 7.2.5 for further details.

¹⁴ Beginning 24 hours before ¹³¹I-omburtamab administration please see section 6.1.2.

¹⁵ Given 1-2 hours prior to ¹³¹I-omburtamab administration, including oral acetaminophen/paracetamol and antihistamine (e.g., diphenhydramine), please see section 6.1.2¹⁶
Drawn and held for culture if elevated body temperature after dosing suggests infection rather than expected response to intracerebroventricular dosing.

¹⁷ Dose reduction: 50% (25 mCi) for patients < 1 of age and 33% (33.5 mCi) for patients age 1 year to < 3 years of age, respectively.

¹⁸ Non-SAE's captured from signing the informed consent form (ICF) to dosing should be recorded as medical history. AEs should be reported until 3 weeks after the last IMP administration. SAE's should be captured from signing the ICF. Starting at week 4 (for patients receiving only one cycle) and starting at week 8 (for patients receiving both cycles) only SAEs considered related to ¹³¹I-omburtamab or new onset of cancers regardless of causality should be reported.

¹⁹ Limit to therapy related to cancer.

²⁰ In case fertile women (experienced menarche prior to screening or during treatment, until week 8) are enrolled; pregnancy testing should take place at screening, at week 4 and week 8, and at follow-up at week 26.

²¹ Follow-up at week 26 (24-29 weeks after first treatment) and Long-term follow-up visits at Weeks 52, 78, 104, 130 & 156 (\pm 4 weeks) can be done at referral site.

²² If done at referral site imaging parameters as required in the Imaging Manual should be followed to the extent possible.

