6 DESCRIPTION OF DESIGN AND TRIAL POPULATION

6.1 Overall trial design and plan

This single-arm, open-label, non-randomized trial includes a screening period followed by treatment and observation periods. At least 32 patients are expected to be enrolled. Before entering the screening period, patients are recommended to have received salvage therapy including surgery, irradiation (preferable craniospinal) and high dose chemotherapy (recommended modalities listed in Appendix 2).

Patients without an objective disease progression (as determined by radiographic examination) 4 weeks after the first infusion and without clinically significant Grade 4 toxicity, are eligible for a second dosing cycle. ^{131}I -omburtamab will be administered via an indwelling intracerebroventricular access device (e.g. Ommaya). In order to avoid an additional procedure and burden to the patient, it can be considered to place the intracerebroventricular access device in connection with the recommended tumor resection procedure (see section 13.4).

After ^{131}I -omburtamab treatment, safety and efficacy will be assessed as described in the flow charts in Table 1 Schedule of time and events with follow-up at week 26 followed by long-term follow up for up to 3 years with regards to survival. An interim analysis, evaluating the dosimetry and pharmacokinetic endpoints as well as available safety and efficacy data, has been conducted on data from patients having received at least treatment cycle 1 (both dosimetry and treatment dose) prior to January 1st, 2020. Starting January 1st, 2020, no further patients will be administered dosimetry doses. After completion of the interim analysis, the dosimetry doses have been removed from treatment cycles. After this, a treatment cycle will take 4 weeks, compared to the previous 5 weeks cycle and will include a treatment dose only followed by an observation period and post-treatment evaluations.

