9.1.2 Secondary endpoints

9.1.2.1 ***CNS/LM Progression-Free Survival (CNS/LM PFS) at 6 and 12 months***

The time frame for CNS/LM PFS will be from first treatment dose of ^{131}I -omburtamab to time of documented CNS/LM progression or death from any cause. CNS/LM PFS will be censored at last date of disease evaluation without evidence of CNS/LM progression. CNS/LM PFS at 6 and 12 months will be estimated using Kaplan-Meier methods.

9.1.2.2 ***OS at 12 months***

OS at 12 months will be estimated by Kaplan-Meier methods following the same time and censoring scheme as the primary endpoint.

9.1.2.3 ***Objective response rate (ORR)***

Response will be assessed at 6 months (week 26 visit) after the first treatment dose of ^{131}I -omburtamab as a combination of best overall partial or complete response at 5, 10, and 26 weeks. Assessments will follow the Response assessment in Neuro-Oncology (RANO) group criteria for parenchymal metastasis (Lin et al, 2015) or as defined by EANO-ESMO for leptomeningeal metastases (Le Rhun et al, 2017). The evaluation comprises MRI scans, CSF cytology, and clinical assessments. ORR at week 26 is defined as the proportion of patients with response at week 26 from the total population of patients with radiographically evaluable disease at baseline.

9.1.2.4 ***Dosimetry and PK analysis for ^{131}I -omburtamab***

An interim analysis, evaluating the dosimetry and pharmacokinetic endpoints as well as available safety and efficacy data, will be conducted on data from patients having received at least one treatment cycle1 (both dosimetry and treatment dose) prior to January 1st, 2020. Starting January 1st, 2020, no further patients will be administered dosimetry doses.

9.1.2.5 ***Performance assessment***

Since most if not all patients will have received prior crano-spinal and/or whole brain irradiation, late side effects for such previous therapies are difficult to distinguish from ^{131}I -Omburtamab inflicted toxicities in CNS. However, to evaluate gross changes in neurological

function, performance test will be conducted during screening and at weeks 26, 52, 78, 104, 130 and 156. The scales to be used are: Lansky < 16 years and Karnofsky \geq 16 years.

9.1.2.6 ***Anti-Drug-Antibodies characterization***

A quantitative assay to assess anti-drug antibodies (ADAs) will be developed. The assay will be developed and validated using “cold” labeled omburtamab (^{125}I -omburtamab).

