9.2.2 CSF for cytology, total protein, glucose and cell count

CSF for cytology, total protein, glucose and cell count should be assessed during screening and at week 4, 8, and 26. If positive, it must be repeated within 4 weeks of the positive sampling.

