9.2.10 Neurotoxicity

Neurotoxicity will be assessed by the National Cancer Institute clinical neurotoxicity criteria during screening and weeks 1, 4, 5, 8, 26. All neurologic abnormalities present prior to ^{131}I -omburtamab infusions will be recorded as medical history. Any neurologic changes during the trial period which meet the criteria for Grade 3 or 4 neurotoxicity will be assessed by the trial physicians as being unrelated, possibly or probably caused by the infusion. In the absence of clear evidence progressive disease (PD), it may be assumed that new signs and symptoms are

treatment related. Any patient that develops Grade 4 neurotoxicity after the IMP infusion is to be discontinued from treatment.

Neurotoxicity also will be assessed clinically and radiographically. Assessment of cranial nerves, gross motor function and sensory function will be performed. Assessment and grading of radiographically cortical atrophy, cerebral ventricular size, white matter changes or other abnormalities will be made by a neuro-radiologist. Altered CSF flow will be interpreted by the trial nuclear medicine physicians.

Clinical neurotoxicity evaluation is to be conducted at screening and weeks 1, 4, 5, 8 and 26, as indicated in the flowchart. The radiographic assessment of neurotoxicity and disease progression (by MRI) is to be conducted at screening, weeks 4 and 8 and week 26 only.

Lansky (Karnovsky for children \geq 16 years) performance score will be analyzed to evaluate gross neurologic function and a measure of a patient's long-term function.

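### The ORR rule leaves the numerator open, cites weeks 5 and 10 that are not in the current schedule, and does not exclude responses first seen after other therapy

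*Combined protocol and SAP*

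**What the plan says.** Section 9.1.2.3 says that response is assessed at the week-26 visit "as a combination of best overall partial or complete response at 5, 10, and 26 weeks". The paragraph ends with a definition: "ORR at week 26 is defined as the proportion of patients with response at week 26", taken "from the total population of patients with radiographically evaluable disease at baseline". The evaluation combines MRI, CSF cytology and clinical assessment. Sections 5.3.3 and 8.1.2 place ORR at 6 months and add nothing on how the numerator is formed.

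The current assessment times are different. Section 9.2.10 says that radiographic assessment of "disease progression (by MRI) is to be conducted at screening, weeks 4 and 8 and week 26 only". Section 9.2.2 says "CSF for cytology, total protein, glucose and cell count should be assessed during screening and at week 4, 8, and 26". In Table 1, week 5 is the cycle-2 dosing visit, without MRI or cytology, and there is no week-10 visit. Section 6.1 explains that "a treatment cycle will take 4 weeks, compared to the previous 5 weeks cycle".

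On later treatment, section 7.3.1 permits further anti-cancer therapy once the MRI after the last dose has been read, which it puts at week 9. Section 7.4 permits any treatment after the product is discontinued. Section 6.9.3 keeps discontinued children in follow-up. Section 6.1.4 allows re-treatment after a CNS/LM relapse. Section 12.3 uses the FAS for all efficacy endpoints and Clopper-Pearson intervals for ORR. The missing-data rules in section 12.9 do not mention ORR. Section 12.1 defers detail to an SAP, but no separate SAP text is available here.

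**The concern.** Two statisticians could follow section 9.1.2.3 in good faith and report different response rates from the same data. One would count a child whose partial response was seen after cycle 1 and lost before week 26, and the other would not. Both would have to decide what weeks 5 and 10 mean for a child on 4-week cycles. Both, reading literally, would count a response that first appeared after a different treatment.

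The trial is open-label and single-arm, and section 6.1 says that an interim analysis of available efficacy data has already been done. A numerator that is still open can be settled after responses are known. A response to later therapy could also be credited to the product.

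**Working it through.** The documents give no ORR assumption, number of evaluable children, or power for ORR, so there is no stated figure to reproduce. The check compares the passages and adds an illustration.

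**1. Numerator.** Four courses under the two readings:

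| Course | Best overall through week 26 | Present at week 26 |
|---|---|---|
| Early response, still present at week 26 | counts | counts |
| Early response, progression before week 26 | counts | does not count |
| First response at week 26, no other therapy | counts | counts |
| First response at week 26, after other therapy | counts | counts |

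The second row separates the readings. The fourth shows that later therapy is a separate gap, because neither reading excludes that child.

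**2. Assessment weeks.** Table 1, footnote 7, gives the week-4 and week-8 MRI a window of ±4 days. Week 5 is 7 days after week 4 and week 10 is 14 days after week 8, so both fall outside it. Two 5-week cycles end at weeks 5 and 10, so these weeks probably remain from the former cycles. That is an inference from section 6.1; the former MRI and cytology weeks are not given. Calendar weeks also move when cycle 2 is delayed. Section 6.1.4 allows up to 8 weeks, and if these are added to the schedule the cycle-2 evaluation falls at 8 + 8 = week 16.

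**3. Time for other therapy before the week-26 visit.** Table 1, footnote 21, puts that visit at 24 to 29 weeks after first treatment.
- From week 9 (section 7.3.1): 24 − 9 = 15 to 29 − 9 = 20 weeks.
- From week 4, for a child who stops after cycle 1 (sections 6.9.3 and 7.4): 24 − 4 = 20 to 29 − 4 = 25 weeks. This takes section 7.4 as governing once the product is stopped; if the week-9 limit in section 7.3.1 still applied, the first range would hold.
- Re-treatment is a narrow route. Relapse at week 8 followed by the full 12-week course in Appendix 2, which is discretionary, puts the new infusion near week 20. Table 1 evaluates a week-1 infusion in week 4, so the evaluation is near 20 + 3 = week 23.

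Section 7.3.1 refers to an MRI at week 9, while the schedule has it at week 8. These passages must be reconciled.

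**4. Size.** Each reclassified child moves ORR by 100/n points, where n is the number evaluable at baseline:
- n = 50 (enrollment maximum, section 6.8): 2.0
- n = 32 (planned minimum): 3.1
- n = 20 (assumed): 5.0
- n = 10 (assumed): 10.0

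Illustration with n = 20 (all counts assumed): 8 children respond at some time, 2 of them lose the response by week 26, and 1 of the remaining 6 first responded after other therapy. Exact 95% limits in brackets:

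| Numerator | Response after other therapy counted | Not counted |
|---|---|---|
| Best overall | 8/20 = 40.0% (19.1–63.9) | 7/20 = 35.0% (15.4–59.2) |
| Present at week 26 | 6/20 = 30.0% (11.9–54.3) | 5/20 = 25.0% (8.7–49.1) |

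The same 40% against 30% at n = 50 is 20/50 (26.4–54.8) against 15/50 (17.9–44.6). If no response is lost and no other therapy starts before week 26, all versions agree.

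**The case against.** The strongest reply is that section 9.1.2.3 contains one rule. Its first sentence says how response is put together at the week-26 visit, and its last sentence uses that result. Sections 5.3.3 and 8.1.2 fit this. The reading is natural, so a reader who infers two irreconcilable definitions goes too far. But the text does not state the reconciliation, and the last sentence taken alone describes response at one time point.

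A reader might also infer that the rule cannot be applied at all. It can be, under best overall response, by using whatever scheduled evaluations exist. What stands is that the weeks named are wrong for the current schedule. They may be right for children treated under 5-week cycles.

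On later therapy, the SAP and the two cited sets of response criteria might already exclude such responses. Neither can be checked here, so the documents do not support saying that no rule exists. The per-protocol analysis is not an answer, because permitted therapy is not a protocol violation.

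It may also be tempting to count every child who starts new therapy as a non-responder at week 26. The documents do not require this. A response documented before permitted therapy and still present is a different case from one first seen afterwards, and how to treat it is a choice for the sponsor.

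Finally, the effect is hypothetical and the intervals in the illustration overlap heavily. That is fair. The overlap shows how imprecise ORR will be, but it does not settle which children should be counted.

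**Conclusion.** The ORR rule is wrong as written and should be corrected. The numerator is ambiguous, the early assessment weeks do not match the current schedule, and a literal reading credits responses first seen after other permitted therapy. Confidence is high on the first two parts. It is moderate on the third, because the SAP or the cited criteria may supply the missing rule.

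The per-child shift of 100/n is exact. The responder counts in the illustration and the n values of 20 and 10 are assumptions, and the true gap may be zero. A reader should not infer that the main result is at risk: ORR is a secondary endpoint with no threshold or power in the available text, and the 3-year overall survival analysis does not use it.

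**What to change.** 1. State in section 9.1.2.3 whether the numerator is best overall response through week 26 or response present at week 26, and report the other beside it. Record the date of the choice. Section 12.7 names CNS/LM PFS at 6 months as the interim's primary efficacy endpoint and does not say whether ORR was examined.
2. Replace weeks 5 and 10 with the post-cycle-1 and post-cycle-2 evaluations, plus week 26. In the current schedule these are weeks 4 and 8. Use the actual evaluation date when cycle 2 was delayed or the child was treated under the former cycles.
3. Unless the SAP or the cited criteria already do so, leave out of the main ORR numerator any complete or partial response first documented after new anti-cancer therapy or re-treatment. Keep these children in the denominator and add a sensitivity analysis that ignores new therapy. State how a child whose response was documented before new therapy is classified.
4. Keep the stated denominator of children with radiographically evaluable disease at baseline.

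The cost is wording in the protocol and SAP. MRI, cytology and later cancer therapy are already recorded (Table 1 and its footnote 19, and section 7.3.1). The reported ORR may be slightly lower.

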8.1.2 Secondary endpoints

1. CNS/LM PFS at 6 and 12 months will be estimated based on the time from first treatment dose to CNS/LM progression or death from any cause. Patients alive without CNS/LM progression at time of analysis, will be censored at last date of disease evaluation without evidence of progression.
2. OS at 12 months will be estimated based on the time from first treatment dose to death by any cause. Patients alive at time of analysis, will be censored at last date known to be alive.
3. ORR assessed as a combination of partial response and complete response as defined by the Response assessment in Neuro-Oncology (RANO) group criteria for brain metastasis (Lin et al, 2015) or leptomeningeal metastases as defined by EANO-ESMO criteria (Le Rhun et al, 2017). ORR will be assessed at 6 months after the first treatment dose of ^{131}I -omburtamab
4. ORR according to CSF cytology. Response is defined as a complete response when CSF converts from positive at baseline to negative after treatment with ^{131}I -omburtamab
5. Whole-body, organ, blood, and CSF radiation dosimetry.
6. Pharmacokinetic analysis of activity in blood and CSF including derivation of best-fit uptake and/or clearance parameters (half-times, maximum value) of time-activity concentration curves and of I-131 residence times (i.e., cumulated activity) concentrations (in $\mu\text{Ci}\cdot\text{h/g}$).
7. The frequency, type, and duration of treatment-emergent severe adverse events and serious adverse events, including clinically significant laboratory abnormalities. All adverse events will be graded according to Common Terminology Criteria for Adverse Events (CTCAE), version 4.0.
8. Performance assessment to monitor gross changes in neurological function is performed at week 26 and subsequently every 6 months during trial period.
9. The rate of ADA occurrence assessed three weeks after the first and second treatment dose of ^{131}I -omburtamab

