12.2 Populations of Interest

- Full Analysis Set

The full analysis set (FAS) will include all patients enrolled in the trial who begin an infusion of ^{131}I -omburtamab

- Per Protocol Analysis Set (PPS)

The PPS will include all FAS patients who have no major protocol violations.

Additional patients with other protocol violations may be uniformly excluded on the basis of data review. The precise reasons for excluding patients from the PPS will be fully defined and documented before data lock

- Safety Analysis Set

The safety analysis set will include all enrolled patients who receive at least one dose of IMP

- External control group

External controls will be primarily obtained from a query to the Central German Childrens Cancer Registry (CGCCR). CGCCR initiated in 1980, registers approximately 2,000 children per year who are diagnosed with a malignant disease. CGCCR receives patient data from all paediatric oncology centers across Germany. 99% of all paediatric patients diagnosed with cancer in Germany were included in the national trials, with continuous update of the clinical data within the CGCCR.

The CGCCR data will be used to obtain an estimate of the 3-year survival rate in a contemporary systemically treated cohort of children. To explore the development of systemic treatment we will employ cut-offs in 2000 and 2004.

[REDACTED]

[REDACTED]

[REDACTED]

[REDACTED]

[REDACTED]

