12.3 Efficacy Analysis

The FAS will be used for all efficacy endpoints. Additionally, the primary and secondary endpoint analyses will also be performed on the PPS. The primary endpoint of the OS rate at 3 years as well as OS at 12 months, and CNS/LM PFS at 6 and 12 months with corresponding 95% confidence intervals, will be estimated using Kaplan-Meier methods using the FAS. The comparison to external controls (OS only) will be exploratory and performed using multiple cox regression taking into account the most important prognostic factors identifiable in the historic data. The median OS and CNS/LM time and associated 95% confidence interval will be calculated. Results will be displayed with Kaplan Meier plots. ORR according to RANO criteria and CSF cytology as well as CSF cytology alone, will be assessed, 95% confidence intervals will be calculated using the Clopper-Pearson exact methodology.

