Appendix 2 Salvage Treatments Recommended Prior to Trial 101 Entry*

Time	Treatment
Week -12	Resection of CNS disease when possible
Week -11	Irinotecan 50 mg/m ² /dose IV daily x5
Week -10	Craniospinal irradiation 2160 cGy/boost at tumor bed to 3000 cGy **
Week -5	Irinotecan 50 mg/m ² /dose IV daily x5
	Temozolamide 250 mg/m ² /dose daily x5
	Carboplatin 500 mg/m ² /dose daily x2 (only if systemic NB present)
	Stem cell rescue ***
Trial start	First administration of IMP

* all salvage treatments will be depending on patient's condition and are ultimately at the treating physician's discretion

** to be acknowledged and agreed to by the local radiation-oncologist. For patients with unifocal resected CNS disease, a reduction in the craniospinal radiation dose to 1800cGy is recommended

*** if needed

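### The ORR denominators are not reconciled between sections 9.1.2.3 and 12.3 and do not match how response is judged

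*Combined protocol and SAP*

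**What the plan says.** Section 9.1.2.3 defines the main ORR as a proportion "from the total population of patients with radiographically evaluable disease at baseline". It applies RANO criteria to parenchymal metastases and EANO-ESMO criteria to leptomeningeal metastases, and adds: "The evaluation comprises MRI scans, CSF cytology, and clinical assessments".

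Section 8.1.2 lists a second response endpoint based on cytology alone: "Response is defined as a complete response when CSF converts from positive at baseline to negative after treatment with" the product. It gives no denominator.

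Section 12.3 opens with "The FAS will be used for all efficacy endpoints". On response it says "ORR according to RANO criteria and CSF cytology as well as CSF cytology alone, will be assessed" and "95% confidence intervals will be calculated using the Clopper-Pearson exact methodology", again without a denominator. Section 12.2 puts no condition on baseline disease: "The full analysis set (FAS) will include all patients enrolled in the trial who begin an infusion of" the product.

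Three further places bear on who can respond:

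- Section 6.1 and Appendix 2 recommend salvage therapy before entry, starting with "Resection of CNS disease when possible" at week -12, then irradiation and chemotherapy. A footnote to Appendix 2 leaves all of it to the treating physician.
- Section 6.1.1 places baseline MRI and CSF cytology in the 3 weeks before the first dose, so after any salvage therapy.
- Section 6.9.1 requires CNS or leptomeningeal relapse or progression, but not disease that is still evaluable at screening.

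**The concern.** A response rate is interpretable only if its denominator holds the patients who could have responded by the criteria that define its numerator. Here the link is loose in three places.

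1. The main ORR admits patients on imaging alone, while response is judged partly on cytology. A child with CSF-only leptomeningeal disease can be assessed under the criteria but is not in the denominator. If such a child's response were counted in the numerator anyway, the rate would be inflated.
2. The general FAS sentence in 12.3 and the specific definition in 9.1.2.3 are never tied together.
3. For the cytology ORR, the FAS sentence is the only denominator on offer. A child who is CSF-negative at baseline cannot convert, and so could only dilute the rate.

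At stake are two reported secondary rates, in a trial whose title indication includes leptomeningeal metastases. The same data could give materially different figures depending on how the sections are read.

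**Working it through.** **No figure to reproduce.** The documents state no ORR target, ORR power or expected number evaluable. All counts below are assumptions, except the minimum of 32 and maximum of 50 enrolled (section 6.8).

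**Method.** For x responders among n patients the rate is x/n. The exact 95% interval, which is the plan's own method, runs from the 0.025 quantile of Beta(x, n - x + 1) to the 0.975 quantile of Beta(x + 1, n - x).

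**Step 1: main ORR, evaluable subset against whole FAS.** With m evaluable patients in an FAS of N and response rate r among the evaluable, the whole-FAS rate is r × m/N. The gap is r × (1 - m/N).

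| Assumed counts, N = 32 | Evaluable denominator | Whole-FAS denominator |
|---|---|---|
| 12 evaluable, 4 respond | 4/12 = 33.3% (9.9 to 65.1) | 4/32 = 12.5% (3.5 to 29.0) |
| 20 evaluable, 6 respond | 6/20 = 30.0% (11.9 to 54.3) | 6/32 = 18.8% (7.2 to 36.4) |
| 24 evaluable, 12 respond | 12/24 = 50.0% (29.1 to 70.9) | 12/32 = 37.5% (21.1 to 56.3) |
| 32 evaluable, 16 respond | 16/32 = 50.0% (31.9 to 68.1) | the same |

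For m/N from 25% to 75% and r from 25% to 50%, the smallest gap is 0.25 × 0.25 = 6.25 points and the largest is 0.50 × 0.75 = 37.5 points. At N = 50, with whole-number counts, the range is again about 6 to 38 points. If every child is evaluable, the gap is zero.

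**Step 2: CSF-only leptomeningeal disease.** Assume N = 32: 16 evaluable on MRI with 8 responders, 6 with CSF-only disease and 3 responders, and 10 with no evaluable disease.

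| Rule | Rate (95% CI) |
|---|---|
| Imaging-evaluable only, numerator and denominator | 8/16 = 50.0% (24.7 to 75.3) |
| Any evaluable disease, numerator and denominator | 11/22 = 50.0% (28.2 to 71.8) |
| All responders over whole FAS | 11/32 = 34.4% (18.6 to 53.2) |
| All responders over imaging-evaluable only | 11/16 = 68.8% (41.3 to 89.0) |

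The last row is the inflation that a cytology-inclusive numerator over an imaging-only denominator would produce: 68.75 - 50.0 = 18.75 points.

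**Step 3: cytology ORR.** Response requires a positive CSF sample at baseline. If 8 of 32 are positive (assumed) and 4 convert, the rate is 4/8 = 50.0% (15.7 to 84.3) among those who can convert, and 4/32 = 12.5% (3.5 to 29.0) over the FAS. The 24 CSF-negative children could never have been responders.

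**Step 4: is a mixed population foreseeable?** Salvage is recommended, baseline assessment follows it, and evaluable disease is not an entry criterion. Children with none at baseline can therefore enrol. How many will do so cannot be derived from the documents.

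**The case against.** The strongest defence is that the two sections nest. The FAS is an analysis set, 9.1.2.3 is a specific endpoint definition, and together they give FAS patients with evaluable disease. The wording of 12.3 gives some support: it names the FAS again for the Kaplan-Meier endpoints but not in its ORR sentence. Restricting ORR to evaluable disease is also a sensible answer to pre-entry salvage. This stands in part. It is a natural reading and close to the fix proposed here, but no text states it. It does not repair the mismatch between an imaging-only denominator and criteria that use cytology, and it supplies no denominator for the cytology ORR.

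A second defence is that the cytology ORR already covers CSF-only disease. That is correct, so these children are not lost to response evaluation. They are outside the main ORR only, and the endpoint that does cover them lacks a stated denominator. Its definition builds in baseline positivity for the numerator and is silent on who is divided by.

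A third is that section 12.1 leaves detail to the SAP. The text available contains no further ORR rule, so whether one exists elsewhere cannot be checked.

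A reader might go further and infer any of the following. The documents support none of them.

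- **The plan contradicts itself outright.** The nested reading is open, so the sections are unreconciled rather than certainly contradictory.
- **The plan counts children without disease as failures.** No passage says so. It follows only if the general FAS sentence overrides the specific definition.
- **Many children will enter with no visible disease.** Salvage is discretionary and resection depends on feasibility. Section 9.1.2.5 expects most patients to have had prior irradiation, but that does not show how many lack residual disease.
- **The rate would reflect prior salvage rather than the product.** This is not shown for the imaging-evaluable denominator. The dilution arises only when the whole FAS is the denominator.

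**Conclusion.** The point holds as one of unreconciled and mismatched denominators for two secondary endpoints. The main ORR admits patients by imaging but judges them partly by cytology. The cytology ORR has no denominator except the general FAS rule, which would include children who cannot convert. No rule classifies children without evaluable disease at baseline.

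The size is unknown because the number evaluable is not given. Under the assumed ranges of 25% to 75% evaluable and 25% to 50% response, the choice between evaluable subset and whole FAS moves the rate by about 6 to 38 points. It moves it by nothing if all are evaluable. Putting CSF-only responders in the numerator alone would add about 19 points in the illustration.

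The documents attach no threshold or hypothesis to ORR, so no stated decision rule turns on it. The primary analysis of 3-year overall survival is not affected.

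**What to change.** Amend sections 9.1.2.3 and 12.3 to say:

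- The main ORR is analysed in FAS patients with disease evaluable at the last pre-dose assessment by the criterion that applies to them. That means MRI-evaluable disease for parenchymal metastases, and MRI-evaluable and/or CSF-positive disease for leptomeningeal metastases. The same patients define numerator and denominator.
- The radiographic-only subset is also reported.
- The cytology ORR is analysed in FAS patients who are CSF-positive at baseline.
- Patients without evaluable disease at baseline are reported separately as not evaluable for response, with their number.
- The general FAS sentence in 12.3 refers to these definitions for the two ORRs.

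No new data are needed. Table 1 already schedules MRI and CSF cytology at screening, and section 9.2.6 records whether metastases are parenchymal, leptomeningeal or both. The cost is a wording change and rates based on fewer patients than the FAS, with wider intervals. In the step 2 illustration the interval is 28.2% to 71.8% on 22 patients, against 18.6% to 53.2% on 32. It is narrower than the 24.7% to 75.3% from the 16 imaging-evaluable patients alone.
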